20200826	Sections 1, 5, 11.1, 11.4.2, 11.5.1, 11.5.2, 11.5.4, 11.5.5, and 16.4	Updated investigators. Definition of unacceptable toxicity revised per FDA request under IND (Sections 1, 11.5.4). New abbreviation added (Section 5). Language added regarding how indeterminate MGMT methylation will be handled (Section 11.1). Updates to safety precautions (Sections 11.1, 11.4.2). Revised CRS Management Plan per FDA request under IND (Section 11.5.1). New section added regarding use of reduced dose of bevacizumab for inflammatory response (Section 11.5.2). CTCAE version clarified as 4.03 (Sections 11.5.4, 11.5.5, 16.4)		

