11.5.3 Allergy Testing

Patients who experience a hypersensitivity reaction as described in Section 15.3 may be offered optional Allergy Testing. To complete the optional Allergy Testing, patients must sign the Allergy Test Consent Form. Allergy testing will only be done on patients who have experienced a hypersensitivity reaction following vaccine administration, in an attempt to uncover which specific element of Component A and/or Component B results in the

reaction. Patients will receive intradermal injections of potential allergens to both the left and the right groin. The allergens include components that are present in Component A and Component B of the PEP-CMV vaccine, as relevant. Each intradermal injection will be administered 1 hour apart and blood draws (~20 mL) will be taken 1 hour prior to the first injection and 1 hour following the final injection. Blood (~20 mL) will be drawn to monitor immune activity through analysis of TNF α , GM-CSF, IFN α , IFN γ , IL-6, and IL-1, as appropriate. Patients will receive SLP and Montanide in the right groin and GM-CSF, gB, and KLH in the left groin. If the patient has only received either Component A or Component B, they will only receive intradermal injections of the elements that were part of the vaccine that they received. Patients will be monitored according to Allergy and Immunology standard of care practices in the clinic.

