11.5.4 Unacceptable Toxicities

The original definition of unacceptable toxicities in this study was any vaccine-related or any non-neurologic \geq Grade 3 toxicity of any duration not attributable to TMZ, bevacizumab, and/or disease progression; any Grade 4 toxicity, including neurologic events not due to progressive disease; or any life threatening-event not attributable to concomitant medication, co-morbid event, or disease progression. The definition of unacceptable toxicity was revised with v.20200117 of the protocol and will be defined now as any life-threatening \geq Grade 3 toxicity that is possibly, probably, or definitely related to the PEP-CMV vaccine with the following exceptions (updated in the v.20200504 protocol). A portion of the Grade 3 vaccine reactions noted in prior patient experiences with the PEP-CMV vaccine, described in Sections [11.5.1](#) and [14.2.1](#), will not be considered unacceptable if they are indicative of immune response. That is, toxicities such as Grade 3 flu-like symptoms, fever, and chills/rigors will not be considered unacceptable toxicities if the duration is less than 72 hours. Please see Section [11.5.1](#) for guidelines on management of immune response, including cytokine release syndrome (CRS). Any \geq Grade 3 organ toxicity (cardiac, renal, hepatic), including CRS-related toxicities such as hypotension and tachycardia, of any duration will be considered an unacceptable toxicity. Toxicities will be tracked on all subjects who received PEP-CMV vaccine using the NCI CTCAE (Version 4.03) criteria. Patients who experience unacceptable toxicities will not continue to receive vaccine therapy. Although not considered an unacceptable toxicity, any patient with \geq Grade 2 urticaria will not receive further vaccines, will be withdrawn from the study, and will be replaced if less than 3 vaccines have been administered without unacceptable toxicity.

The prevalence of unacceptable toxicities occurring during the initial 3 bi-weekly vaccinations or the vaccinations administered concurrently with temozolomide will be continuously monitored. If more than 25% of accrued patients experience unacceptable toxicities, then accrual will be suspended and reported toxicity will be carefully reviewed to determine if modifications to the protocol treatment should occur. Peptide vaccinations employing Montanide ISA-51 as adjuvants have generally been well tolerated in human patients in numerous phase I-III trials.

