14.2 Potential Risks

14.2.1 Allergic Reactions to PEP-CMV Immunization

Injection of the PEP-CMV vaccine may result in an allergic reaction, which could include redness and swelling at the injection site, itching, hives, low blood pressure, difficulty breathing, or in the most extreme circumstances, death. In addition, if the immune system becomes overly activated, potential discomforts locally may include pain, redness and swelling at the injection site. Grade 3 vaccine reactions have been experienced by patients

who have received the PEP-CMV vaccine in this study and include hypotension, flu-like symptoms, and lactic acidosis. Patients also have experienced Grade 1 and 2 vaccine reactions, such as fever, chills, headache, sinus tachycardia, nausea, and dehydration. Our recent analysis of patients with AEs on this study indicates that pp65-specific T cell activation may be inducing a temporary elevation of pro-inflammatory cytokines. We believe that the vaccine reactions we have been observing in PERFORMANCE are likely indicative of vaccine potency. Patients who have demonstrable Grade III reactions also have measurable cellular responses to the PEP-CMV vaccines, which may be indicative of clinical responses.

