If 2 out of 3 Schedule B patients experience hypersensitivity reactions after Component A injection during Vaccine #2, but Schedule A patients have not experienced hypersensitivity reactions after Vaccine #1, Schedule B patients will discontinue the use of Component B and continue all further vaccinations with Component A alone.

If 2 out of 3 patients from both Schedule A and B experience hypersensitivity reactions after Vaccine #1, the study will be put on hold and the study team will work on modifying the study drug to decrease the hypersensitivity reaction.

Overall Adverse Event Monitoring: The prevalence of unacceptable toxicities occurring during the initial 3 bi-weekly vaccinations administered concurrently with temozolamide will be monitored. If more than 25% of accrued patients experience unacceptable toxicities, then accrual will be suspended and reported toxicity will be carefully reviewed to determine

if accrual should be terminated or modifications to the protocol treatment should occur. This review will consider that patients will have different lengths of follow-up and duration of vaccination treatment.

As described in Section 11.5.3, the definition of unacceptable toxicity has been modified with v.20200117 of the protocol, and now excludes vaccine reactions indicative of immune response. Therefore, as of the time of this amendment, no patient had experienced an unacceptable toxicity under the new definition.

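### Section 15.3 reports zero unacceptable toxicities under a superseded definition and a wrong cross-reference; the zero cannot be carried forward under the current Section 11.5.4

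*Combined protocol and SAP*

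**What the plan says.** Under Overall Adverse Event Monitoring, Section 15.3 suspends accrual for review if more than 25% of accrued patients have an unacceptable toxicity. The section says that this is the only part of its monitoring still applicable after the 20190312 amendment. It continues: "As described in Section 11.5.3, the definition of unacceptable toxicity has been modified with v.20200117 of the protocol", adds that the definition now leaves out vaccine reactions that indicate an immune response, and concludes: "Therefore, as of the time of this amendment, no patient had experienced an unacceptable toxicity under the new definition".

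The section it cites is headed "11.5.3 Allergy Testing". The definition stands under "11.5.4 Unacceptable Toxicities". That section attributes a revision to v.20200117 and then dates its carve-outs: "with the following exceptions (updated in the v.20200504 protocol". The carve-outs cover Grade 3 flu-like symptoms, fever and chills or rigors lasting under 72 hours, introduced as examples. The section then says that any organ toxicity of Grade 3 or above is treated differently, "including CRS-related toxicities such as hypotension and tachycardia, of any duration will be considered an unacceptable toxicity". The synopsis carries the same two rules.

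Section 14.2.1 records that Grade 3 vaccine reactions have occurred in patients "who have received the PEP-CMV vaccine in this study and include hypotension, flu-like symptoms, and lactic acidosis".

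Section 15.4.1 makes the percentage of patients with unacceptable toxicity the primary safety estimate, within arm and by period of study conduct, in all patients who received any vaccine.

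**The concern.** The wrong section number alone would be clerical. The sentence that depends on it is not, because Section 15.3 and Section 11.5.4 can classify the same event in opposite ways. Section 11.5.1 attributes the observed reactions to CRS and regards them as signs of vaccine potency. On Section 15.3's description, a Grade 3 hypotension of that kind is a reaction indicative of immune response and is left out. On the current Section 11.5.4 it is CRS-related hypotension and is counted.

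Two things depend on that classification: the numerator of the primary safety percentage, and the numerator of the only numeric accrual rule still in force. A statistician who works from Section 15.3 alone would have the wrong definition and a count that belongs to an earlier version of the protocol.

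**Working it through.** **1. Can the zero be reproduced?** No. The full v.20200117 definition and the patient-level events are not in the documents. On Section 15.3's own summary of that definition, the count is 0 only if every Grade 3 vaccine reaction was classed as indicative of immune response.

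**2. Order of the texts** (the amendment log is used for dating only).
- v.20200117: the definition is revised, and the history of vaccine reactions is added to Sections 11.5.1 and 14.2.1. The reactions listed in 14.2.1 therefore appear to have been known when the zero was written.
- v.20200504: the carve-outs are updated, according to Section 11.5.4 itself.
- 20200826: "Definition of unacceptable toxicity revised per FDA request under IND (Sections 1, 11.5.4"). That entry also adds a new Section 11.5.2, which would explain why the definition moved from 11.5.3 to 11.5.4. Section 15.3 is not among the sections it lists as changed.

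**3. Reported Grade 3 reactions against the current Section 11.5.4.**

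| Grade 3 reaction in 14.2.1 | Current 11.5.4 and synopsis |
|---|---|
| Flu-like symptoms | Exempt if under 72 hours |
| Hypotension | Named as counted, any duration |
| Lactic acidosis | Not named; the exempt list is open-ended, so undetermined |

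On this reading at least one vaccinated patient has a countable event. The reading assumes that the sentence on organ toxicity stands on its own. Section 11.5.4 opens its definition with the qualifier *life-threatening*, which the synopsis lacks.

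**4. What one event would mean.** The smallest count above 25% of n patients is floor(0.25 × n) + 1. Intervals are exact (Clopper-Pearson) 95% intervals.

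*Base of 15*: Component-A-only patients as of 20200110 (Section 15.1).
- 0.25 × 15 = 3.75, so the rule trips at 4: 3/15 = 20.0%, 4/15 = 26.7%.
- One event: 1/15 = 6.7% (0.2% to 31.9%). Zero events: 0% (upper limit 21.8%).

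*Base of 26*: all vaccinated patients, an assumption built from Section 15.1 as 15 + 3 (initial randomized) + 6 (safety cohort) + 2 (resumed, received Component B) = 26. That it equals the target of 26 evaluable patients is a coincidence.
- 0.25 × 26 = 6.5, so the rule trips at 7: 6/26 = 23.1%, 7/26 = 26.9%.
- One event: 1/26 = 3.8% (0.1% to 19.6%). Zero events: 0% (upper limit 13.2%).

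**5. What cannot be filled in.** Section 14.2.1 gives no number of patients, vaccine number, component or arm for the hypotension. The event may lie outside the Component-A-only group or outside the monitored window. That window is itself worded differently: Section 15.3 covers the first three bi-weekly vaccinations given with temozolomide, while Section 11.5.4 and the synopsis cover the first three or those given with temozolomide. The start of Section 11.5.1 was not in the text available for this review and may hold these details; its absence is not held against the plan.

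**The case against.** The strongest reply is that the zero carries its own date. It refers to the time of the amendment and to the definition then new, and a later definition cannot make a historical statement false. This stands. A reader might infer that the sponsor misreported the count in January 2020, and the documents do not support that.

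Second, no passage makes the sentence a starting value for anything. Section 11.5.4 tracks toxicities in every vaccinated patient and monitors them continuously, and Section 15.4.1 computes the safety percentage from all vaccinated patients. A reader might infer that the primary safety figure or the 25% rule has been understated. Nothing shows that an event was left uncounted once the definition changed, so that inference fails too.

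Third, the *life-threatening* qualifier in Section 11.5.4 could be read to narrow the whole definition, so that some Grade 3 hypotension would not count. The later sentence in the same section and the synopsis favour the broader reading, but the text is not settled. This is a reason to reconcile the passages, not to leave them.

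Fourth, the 25% rule is not the only protection. Section 14.3 requires action on an unexpected frequency of Grade III or IV events, and the plan provides for a Safety Oversight Committee and a DSMBplus. That is correct and lowers the stakes for patient safety. It does not settle how the primary safety endpoint is counted.

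**Conclusion.** Section 15.3 is stale. It cites the wrong section, describes the definition by its v.20200117 form, and gives a zero that cannot be carried forward under the current Section 11.5.4 and synopsis, because Section 14.2.1 reports Grade 3 hypotension on study. This rests on two assumptions: that the organ-toxicity sentence in Section 11.5.4 is not limited by the earlier qualifier, and that the hypotension, which Section 14.2.1 lists as a vaccine reaction, is at least possibly related to the vaccine.

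The size is unknown. Each reclassified patient adds 6.7 percentage points on a base of 15 or 3.8 on an assumed base of 26, against triggers of 4 and 7 patients. It would be tempting to conclude that accrual should already have been suspended. The documents give neither the number of cases nor the denominator needed, and nothing in them shows that the trigger was reached or nearly reached.

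**What to change.** - Change the reference in Section 15.3 from 11.5.3 to 11.5.4.
- Reconcile the definition across Section 15.3 (which summarises it as leaving out immune-indicative reactions), Section 11.5.4 (which has the *life-threatening* qualifier) and the synopsis (which does not). Which wording should govern is for the sponsor and its clinical and regulatory advisers.
- Re-adjudicate existing Grade 3 or higher vaccine-related events under the reconciled definition.
- Either label the zero as applying to v.20200117 only, or replace it with a count that carries its cut-off date.
- State the denominator for the 25% rule (Component-A-only patients or all vaccinated patients), and use one wording for the monitored vaccination window.

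Reporting by arm and by study period is already planned in Section 15.4.1 and needs no addition. The cost is a re-review of what should be a few event records and a short text amendment. The safety figure may turn out less favourable than the present sentence suggests.

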15.4 Analytic Methods

15.4.1 Primary Analyses

Safety: To assess the safety of PEP-CMV vaccination in combination with adjuvant TMZ, the percentage of patients with unacceptable toxicity will be estimated within each arm. All patients who received any PEP-CMV vaccine will be included in these safety analyses.

As described in Section 15.1, the vaccination treatment regimen has been modified over time due to safety issues. Hence, toxicity will be summarized for each period of study conduct as follows:

- Initial randomization period where patients were assigned to one of two TMZ regimens with both Component A and B. The 2 patients assigned to standard TMZ after randomization resumed who received both Component A and B will also be included in this summary.
- Safety Cohort Period in which all patients received standard TMZ with vaccine Component A and B
- Randomization period in which patients received at least one cycle of Component B prior to discontinuation
- Randomization period in which patients are assigned to one of two TMZ regimens and receive only vaccine Component A

Immunologic Response: The primary analysis will focus on patients who have follow-up immunologic monitoring after the 3rd vaccination and before initiation of the second TMZ/vaccine cycle. Such a patient is considered “evaluable” for the immunologic response primary analyses.

The Wilcoxon rank sum test will compare treatment groups with regard to the median peak number of T cells that secrete IFNy by ELISPOT in response to component A of PEP-CMV. Analyses will include only those patients who have an assessment of immune response after receiving 3 vaccinations.

Though the original vaccination included Component A and B, the primary immunologic analysis will focus on only those patients who received Component A alone. Additional exploratory analyses may include data from the few “evaluable” patients who received both vaccine Components A and B.

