Patients who receive more than 1 cycle of TMZ will be vaccinated in conjunction with each **subsequent** 28-day TMZ cycle for a total of 6 to 12 cycles of TMZ after RT followed by further vaccination up to 20 vaccines. Patients who receive only 1 cycle of TMZ will be vaccinated on a 28-day cycle with up to 20 vaccines. All cycles, with or without TMZ, may be given every 4 (+ 2) weeks, in order to adjust for slight delays on startup of each 28-day cycle, and the total number of cycles are given at the discretion of the treating oncologist. During vaccine (+/- TMZ) cycles, vaccinations will occur on day 23 (-1 day, + 2 days) of each cycle for each arm: (Arm 1) standard TMZ (150-200 mg/m²/day on days 1-5 of each 28-day cycle), or (Arm 2) dose-intensified TMZ (75-100 mg/m²/day on days 1-21 of each 28-day cycle). All vaccines will be given i.d. approximately 10 cm below the inguinal ligament bilaterally. A target of six cycles with a maximum of twelve cycles of TMZ may be given to patients enrolled prior to approval of protocol version 20181218 and those with MGMT/inconclusive methylation status if enrolled after approval of protocol version 20181218, at the discretion of the treating neuro-oncologist. After the completion of a patient's TMZ cycles, vaccines will continue to be administered every 4 (+ 2) weeks for a maximum of 20 vaccines (unless tumor progression occurs).

Patients will be imaged with contrast-enhanced MRI after vaccine 3 (at cycle 2 initiation visit) and then approximately every 8 weeks [every 2 cycles thereafter (i.e., end of cycles 3, 5, 7, 9, 11)]. RANO criteria [111] will be used for assessment of pseudoprogression and patients demonstrating definitive progression will be removed from study. Any patient removed prior to immune monitoring post vaccine 3 will be replaced for immunologic endpoints. Clinical endpoint comparisons will be made amongst patients randomized to adjuvant TMZ treatment arms who have received at least one vaccine.

Blood for immune monitoring will be obtained:

- Prior to Td pre-conditioning
- During vaccines 1 and 2 (just prior to Component A, 1 and 2 hours after Component A)
- Prior to vaccine 3
- After vaccine 3 (within 2 weeks of vaccine 3 [+ 3 days])
- Prior to vaccines 4 and 6
- At tumor progression (if feasible)

Patients seen by the Duke neuro-oncology team between these vaccine visits may have blood drawn for immune monitoring at the discretion of the study team.

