11.8 Definition of Evaluable Subjects, On Study, and End of Study

Subjects evaluable for the analysis of the primary endpoints will include all randomized patients who undergo immune monitoring post vaccine #3, prior to 2nd vaccine/TMZ cycle. Survival analyses will include all randomized patients evaluable for the primary outcome.

Safety analyses will include all patients who receive vaccine treatment.

Once the patient signs an ICF, that subject will be considered “on study”. Rationale for taking patient off protocol treatment (see Section 11.10.1 below) will be documented.

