11.10.3 Replacement of Early Withdrawal(s)

Subjects who voluntarily withdraw prematurely or who are withdrawn by the PI prior to immune monitoring post vaccine #3 will be replaced. However, the data from these patients will be included in all appropriate analyses.

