15.4.3 Exploratory Immunologic Analyses

The following immunologic analyses will focus on patients who are evaluable for the immunologic monitoring primary analysis, i.e., patients who had immunologic monitoring conducted at baseline and prior to the second cycle of TMZ. These analyses will focus primarily upon patients who received only Component A. However, additional analyses may be conducted besides those described below.

Quality of Immune Response: The quality of the immune response will be assessed by polyfunctional flow cytometry. The analysis used here for polyfunctionality will be one that has been successful at distinguishing HIV progressors and non-progressors based on T-cell phenotype [115, 116]. All data will be background subtracted. For each measure, a lower threshold corresponding to two standard deviations above background is set to 0 based on a Poisson model essentially allowing T-cells to be designated as positive or negative for a certain phenotypic marker. The number of positive phenotypic markers post-vaccination will be calculated for each patient. The Kruskal-Wallis test will be used to compare treatment arms with respect to the number of phenotypic markers observed post-vaccination 3, as well as at vaccination 6. Additional exploratory analyses will be conducted using a Fisher's exact test that will compare treatment groups with respect to the proportion of patients with 5 positive markers, and 4 or more positive markers. Analyses similar to those described for the primary immunologic analyses will be used to examine the percentage of tetramer positive cells.

Analysis of covariance will be used to compare treatment groups with respect to the change between baseline and post-vaccination time-points in mean proliferative response and cytokine production, with baseline levels included in the model as a covariate. If assumptions of normality are not satisfied, the Kruskal-Wallis test will be used to compare treatment arms. Analyses will focus on the change between baseline and post-vaccination 3 assessments, as well as the change between baseline and vaccine 6.

Effect on Tregs: The mean levels of Tregs at baseline and at each follow-up assessment will be estimated within each treatment group. A mixed model that accounts for the correlation of repeated measurements within a patient will be used to compare treatment groups with respect to changes in Treg levels over time.

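### Does limiting the primary ELISPOT comparison to patients assessed after vaccine 3, with earlier losses replaced, call for an added analysis?

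*Combined protocol and SAP*

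**What the plan says.** Section 15.4.1 compares the arms on peak IFN-gamma ELISPOT count by a Wilcoxon rank sum test and adds: "Analyses will include only those patients who have an assessment of immune response after receiving 3 vaccinations". Section 11.8 defines the same set: "Subjects evaluable for the analysis of the primary endpoints will include all randomized patients who undergo immune monitoring post vaccine #3". Section 11.1 deals with earlier losses: "Any patient removed prior to immune monitoring post vaccine 3 will be replaced for immunologic endpoints". Since the 20190312 amendment the set is further limited to patients who received Component A alone.

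Four passages bear on the patients left out:

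- Section 15.4.1, safety: in all vaccinated patients, "the percentage of patients with unacceptable toxicity will be estimated within each arm".
- Section 11.8: "Rationale for taking patient off protocol treatment (see Section 11.10.1 below) will be documented".
- Section 11.10.3, on replaced patients: "the data from these patients will be included in all appropriate analyses".
- Section 15.4.3: "The following immunologic analyses will focus on patients who are evaluable for the immunologic monitoring primary analysis", although "additional analyses may be conducted besides those described below".

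In addition, section 15.4.4 describes OS and PFS from randomisation, and section 11.10.2 keeps early withdrawals in survival follow-up unless they refuse it. None of these passages specifies an ELISPOT comparison outside the evaluable set or a by-arm count of non-evaluable patients.

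**The concern.** Randomisation balances the arms at entry. Replacement restores the count to 13 per arm, but not that balance. Some routes out could depend on the arm: patients who cannot tolerate TMZ are withdrawn before vaccination (Synopsis, 11.1). Others could depend on the immune response: unacceptable toxicity and Grade 2 or higher urticaria end vaccination (11.5.4), and progression is a withdrawal reason (11.10.1). Section 14.2.1 says that patients with Grade III reactions have measurable cellular responses.

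This one test answers the second primary objective, namely which regimen yields more IFN-gamma-secreting T cells. If losses were both unequal and related to response, the test could favour one regimen because of who was left in it, and the planned ELISPOT output would not show that. On 20200110 only 8 of 15 Component-A-only patients were evaluable (15.1, 15.2), which makes sizeable loss look plausible.

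**Working it through.** **Inputs from the plan.** One-tailed Wilcoxon rank sum test at 0.025, 13 evaluable per arm, 81% power (15.2).

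**The plan's own figure.** The 81% came from resampling 5 and 10 individual ACT II titers, which are not listed, so it can be neither confirmed nor refuted. Hypothetical datasets that match the stated medians and ranges give power from about 14% to over 99%; 81% lies inside that range. For what follows I use a normal model in which a shift of 1.19 SD gives 81% power.

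**Loss seen so far.** 8/15 = 53% evaluable. The other 7 may include patients who had not yet reached the post-vaccine-3 draw, and no split by arm is given. This is a snapshot and cannot be read as a loss rate.

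**Size of a possible bias.** Loss rates and correlations here are assumptions. Suppose a fraction q of one arm is lost and the tendency to be lost has correlation r with response. The mean of those retained moves by r × φ(z)/(1 − q), where z is the normal quantile for 1 − q. For q = 0.20, z = 0.8416 and φ(z)/0.8 = 0.35, so r = 0.3, 0.5 and 0.8 give 0.105, 0.175 and 0.280 SD.

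Simulated one-sided error with no true difference (13 evaluable per arm after replacement, normal approximation without continuity correction; no loss gives 2.5%):

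| Loss, arm tested as better v other | Who is lost | r = 0.3 | r = 0.5 | r = 0.8 |
|---|---|---|---|---|
| 20% v 0% | low responders | 4.4% | 6.2% | 10.1% |
| 20% v 0% | high responders | 1.4% | 0.8% | 0.4% |
| 20% v 10% | low responders | 3.2% | 4.0% | 5.2% |
| 20% v 10% | high responders | 1.9% | 1.6% | 1.1% |
| 20% v 20% | either | about 2.5% | about 2.5% | about 2.5% |

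With 20% v 0% loss, power at the 1.19 SD shift is 87/92/96% if low responders are lost and 74/70/65% if high responders are lost. The exact test has size 2.2% at 13 per arm; with low responders lost it gives 3.9/5.5/9.4% for 20% v 0% and 2.8/3.5/4.4% for 20% v 10%. Harm therefore needs both a clear imbalance and a link to response. The documents establish neither, and they do not give the direction.

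**Would an added analysis detect it?** The obvious candidate compares the arms at the scheduled pre-vaccine-2 draw (Table 3, footnote 13) in all randomised Component-A-only patients who have it, next to the same estimate in the evaluable subset.

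1. *Coverage.* Patients withdrawn for TMZ intolerance leave before vaccine 1 and have no such sample. Patients stopped after a vaccine 1 reaction receive no vaccine 2 and would ordinarily not have it. The comparison recovers mainly patients lost between vaccine 2 and the post-vaccine-3 visit.
2. *Resolution.* Take 16 randomised and 3 lost in one arm, 13 in the other, and let all three lost patients have the draw. The Hodges-Lehmann shift in the evaluable set differs from that in all patients by 0.09/0.15/0.24 SD on average at r = 0.3/0.5/0.8. With loss unrelated to response, the same difference has an SD of 0.13. It passes the upper 97.5% null limit in only about 8/16/35% of trials.
3. *Timing.* The draw follows one vaccine. In a three-draw model, its power with no loss is 76% if the full arm difference is already present (82% for the evaluable peak), 51% if three-quarters is present and 26% if half is.
4. *Cost.* The draw would have to be assayed in every patient who has it, including about 26 evaluable ones. Section 15.4.1 does not say that the peak already uses it.

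**Definitions.** Section 15.2 asks for a draw before TMZ cycle 2 and gives no vaccine count. Table 3, footnote 7, runs cycle 1 to two weeks after vaccine 3, so this is the section 11.8 set. Section 15.4.3 adds a baseline draw, which is already scheduled for every patient before Td pre-conditioning. The three wordings very probably describe one set.

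**The case for a change.** The best case for a change is that no existing sentence closes the gap. The clause on withdrawn patients' data names no analysis, and the permission for further analyses sits in a section built on the evaluable set. A patient withdrawn for TMZ intolerance before vaccine 1 appears in no planned immune or safety summary. Section 15.3 reports no unacceptable toxicity under the revised definition, but that covers one route only; urticaria, hypersensitivity, TMZ intolerance, progression and investigator discretion are separate. A by-arm table costs almost nothing and is the minimum needed to judge whether loss was balanced.

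All of that is accurate, and the table is worth having. But it is ordinary trial reporting: the arm is known for every randomised patient, and section 11.8 already has the reason for coming off treatment recorded. Its absence from the analysis section does not put it out of reach. The case for a new supportive ELISPOT analysis is much weaker, because that analysis leaves out the routes that motivate it and seldom separates selection from chance. The link to response is also thinner than it first appears: section 14.2.1 says the responses are measurable, not that they are larger, and no passage ties urticaria, progression or TMZ tolerance to ELISPOT magnitude.

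**Conclusion.** No change to the plan is needed. The restriction is a fair choice for an immunogenicity question about a three-vaccine course: a response after vaccine 3 does not exist in patients who never received it. Replacement makes selection possible, but its size and direction are unknown. Under the assumptions above, the effect on one-sided error runs from none (equal loss) through 3.2% to 5.2% (20% v 10%, low responders lost) to 10.1% in an extreme case (20% v none, correlation 0.8); it falls below 2.5% if high responders are lost from the arm tested as better.

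Several features limit the exposure: only TMZ cycle 1 precedes the endpoint, patients known not to tolerate TMZ are excluded at entry, and Grade 3 flu-like reactions shorter than 72 hours are not unacceptable toxicity. The one added analysis on offer would rarely detect the problem in a 26-patient comparison. Analysts can be expected to report numbers randomised, vaccinated and evaluable by arm with reasons, and to read the regimen comparison in that light. The conclusion would weaken if that account showed a marked imbalance between arms.
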